## LIST OF ABBREVIATIONS

AE	Adverse Event/Adverse Experience
CFR	Code of Federal Regulations
CRF	Case Report Form
DSMB	Data and Safety Monitoring Board
FDA	Food and Drug Administration
GCP	Good Clinical Practice
HIPAA	Health Insurance Portability and Accountability Act
IDE	Investigational Device Exemption
IRB	Institutional Review Board
PHI	Protected Health Information
PI	Principal Investigator
SAE	Serious Adverse Event/Serious Adverse Experience
SOP	Standard Operating Procedure
UADE	Unanticipated Adverse Device Effect

## **Study Summary**

v v		
Title	Long term monitoring of patients with cardiac amyloidosis with implantable event monitors	
Running Title	Long term implantable monitors for cardiac amyloidosis.	
IRB Protocol Number	17-006298	
Phase	Pilot	
Overall Study Duration	3 years	
Subject Participation Duration	Approximately six months +31 days if removal	
DurationThere are four specific aims. We seek to determine in wild ty transthyretin amyloidosis (ATTRwt): Specific Aim 1: Burden of conduction system disease and arrhythr specifically sinus node dysfunction, high grade heart block, and A VA, which will identify those who might benefit from a PPM or I Specific Aim 2: Mechanism of SCD (asystole, pulseless electr activity, or sustained VA) and whether this is different in early vs stage amyloidosis. Specific Aim 3: Risk factors for SCA and more specifically wh bradycardia or VA predict SCD, or whether there are imagin 		
Number of Subjects	50	
Diagnosis and Main Inclusion Criteria	Patients with ATTRwt cardiac amyloidosis are included in this study.	
Device	Biomonitor 3 (Utilized not investigational)	
Duration of Exposure	Intended to remain in the body for 6 months pending clinical indications	
Reference therapy	No change in standard of care treatment.	
Statistical Methodology	Pilot Study	

## 1 Introduction

This document is a protocol for a human research study. This study will be carried out in accordance with the procedures described in this protocol, applicable United States government regulations and Mayo Clinic policies and procedures.

#### 1.1 Background

Amyloid cardiomyopathy (AC) results from myocardial deposition of amyloid fibrils. The most common forms of amyloidosis associated with cardiac involvement include (1) AL amyloidosis, an immunoglobulin light chain plasma cell dyscrasia; (2) Transthyretin (TTR-m) an autosomal familial amyloidosis resulting from mutant transthyretin and (3) Transthyretin wild type (TTR-wt) amyloidosis, arising from a wild type transthyretin primarily in older individuals (1,2). The onset of a restrictive cardiomyopathy and progressive heart failure is the primary concern in cardiac amyloidosis, but another problematic aspect is infiltration of the conduction system, causing bradycardia, atrial arrhythmias (AF), and sudden cardiac death (SCD) (1,2).

Conduction disease in AC manifests as high-grade atrioventricular (AV) block and sinus node dysfunction (bradycardia, heart rate <35bpm) and standard clinical indications for pacemaker implantation have been applied (1,3); however, many clinicians hesitate to treat with pacemakers (PPM) due to a perceived higher complication rate. Atrial fibrillation also presents several management dilemmas as AV nodal blocking agents typically utilized for rate control may be poorly tolerated, and data on anti-arrhythmic drug therapy and ablation are limited (4,5). A major limitation of ablation is high rates of AF recurrence in amyloidosis (4), hypothesized to occur because the arrhythmia is believed to arise from diffuse amyloid infiltration in the atrial tissue rather than from the pulmonary veins, rendering targeted ablation to isolate the pulmonary veins less effective. Although ventricular arrhythmias are also prevalent, their role in SCD in amyloidosis is also controversial (4,6-9). A longer term monitoring study with implantable loop recorders in a small number of patients with AL amyloidosis has suggested that bradycardia leading to asystole is the more likely culprit, at least in advanced amyloid cardiomyopathy, but it is not clear if this is also true earlier in the disease process or if it applies to TTR-wt (8).

A particular challenge with TTR-wt is the paucity of data pertaining to arrhythmia risk. Much of the published literature, although also limited in scope and sample size, addresses arrhythmia risk only in AL amyloidosis. TTR-wt cardiomyopathy is characterized by a more indolent course compared to AL, and individuals may present with heart block or atrial arrhythmias prior to the onset of advanced heart failure symptoms and often before the diagnosis of TTR-wt cardiomyopathy (1,2). Advancements in imaging techniques such as cardiac magnetic resonance imaging and technetium pyrophosphate scintigraphy that permit earlier and non-biopsy diagnosis of TTR-wt diagnosis have enhanced the diagnosis of TTRwt cardiomyopathy (10,11). As a result, it appears TTR-wt may be more prevalent than previously known; there is a significant overlap between TTR-wt cardiomyopathy and an ageing population of patients with heart failure with preserved ejection fraction, hypertrophic cardiomyopathy, and those with aortic stenosis undergoing transcatheter valve replacement (12-14). Therefore arrhythmia risk and management in TTR-wt cardiomyopathy will impact an increasingly growing population of patients, with unique risk factors and management challenges that differ from those with other cardiovascular disease.

One reason that arrhythmia management in amyloidosis has been focused on AL amyloidosis was due to the lack of disease modifying therapies for TTR-wt. The recent availability of disease modifying therapies for TTR amyloidosis that improve both symptoms and mortality also presents an opportunity to impact arrhythmia risk and management (15-17). Previous experiences of implantable cardiac device therapy in amyloid cardiomyopathy for arrhythmia management have suggested that earlier implantation may be associated with superior results (7,18). Whether the current therapies targeted towards stabilization and knockdown of circulating TTR will impact existing conduction disease is less clear, but these therapies may halt, delay or prevent onset of more severe disease that would not be amenable to treatment and could influence mortality. The main objective of this study is to identify TTR-wt cardiomyopathy patients at risk for bradycardia or SCD who may benefit from PPM or implantable cardioverter defibrillators (ICD), and to determine whether monitoring of TTR-wt patients undergoing treatment with disease modifying therapies will identify the subgroup of patients who will benefit most from PPM or ICD.

#### 1.2 Device

The device used in this protocol is NOT investigational. Biomonitor 3 is FDA and available on all markets for monitoring of arrhythmias. This protocol will use the device as FDA approved.

Briefly, The Biomonitor 3 is indicated to detect the following cardiac arrhythmias:

- atrial fibrillation
- bradycardia,
- sudden rate drop,
- high ventricular rate (HVR),
- asystole

The Biomonitor 3 is indicated for use in:

- Patients with clinical syndromes or situations at increased risk of cardiac arrhythmias
- Patients who experience transient symptoms that may suggest a cardiac arrhythmia
- The device has not been tested for and it is not intended for pediatric use

## 1.3 Clinical Data to Date

# *Pilot Study Data submitted to FDA resulting in FDA approval of the Biomonitor implantable loop recorder (ILR) device*

The objective of this pilot study was to provide clinical data of the insertion procedure and the sensing quality of BIOTRONIK's second generation of ILR, the BioMonitor 2, a device which is inserted subcutaneously. Data of 30 patients from 5 Australian clinical sites from December 18, 2014 through July 06, 2015 were included. The most common indications for

insertion of the BioMonitor 2 were syncope and symptomatic or asymptomatic atrial fibrillation. The published results demonstrate safety and efficacy of the insertion procedure and the study device.

The next generation device, the Biomonitor 3 device was FDA approved in 2019 and represents an advancement from its predecessor. It is 60% smaller than the Biomonitor 2 device and is preloaded into a single piece injection tool to permit less invasive and easier insertion, including office settings. Injectable implantable loop recorders which can be inserted subcutaneously are the industry standard. Device recordings offer increased signal quality over its predecessor, the Biomonitor 2.

#### 1.4 Study Rationale and Risk/Benefits

#### 1.4.1 Study Rationale

TTR-wt cardiomyopathy has been considered a life limiting, if indolent, and untreatable cause of heart failure in older individuals. For this reason, clinicians have hesitated to treat potentially life threatening arrhythmias, or to consider implantation of cardiac devices (PPM or ICD) which may improve symptoms and impact mortality. The recent availability of disease modifying therapies ushers in a new era of treatment strategies which improve both mortality and morbidity. The goal of the study is to identify patients who would also benefit from treatment of arrhythmias, and who might otherwise have succumbed to complications from arrhythmias, including stroke, sudden cardiac death, or injury from syncope due to bradycardia.

Implantable loop recorders have been used successfully to monitor for arrhythmia burden and to identify causes of cryptogenic syncope and stroke in patients with cardiovascular disease (19,20). The devices can be implanted at low risk and with local anaesthesia and can be inserted in an office setting, and remaining in situ for up to 3 years to permit long term monitoring (21). The device are explanted at the time of battery expiration. Miniaturized implantable loop recorders have been used to document mechanisms of sudden death in late stage AL amyloidosis but have not been routinely utilized especially in TTR-wt (8). Given the perceived high risk for arrhythmias and the lack of robust data on arrhythmia burden, amyloid cardiomyopathy would seem an ideal population to monitor with implantable long-term loop recorders.

An observation from the recently published Transthyretin Amyloidosis Cardiomyopathy Clinical Trial (ATTR-ACT) was the subgroup analysis suggesting greater benefit in less severe heart failure (17,22). Arrhythmia risk (AF, heart block, and cardiac arrest) might be different in patients with earlier stages of the disease, and if treatment with tafamidis might prevent further progression of conduction system disease and arrhythmia burden. The current study proposed is a pilot study and will not be powered to ascertain the effects of tafamidis on arrhythmia burden in different stages of disease, but observations from the study will provide preliminary data for future and necessary prospective monitoring studies.

Despite high risk of SCD, appropriate risk stratification in amyloid cardiomyopathy is lacking. Traditional risk stratification with decreased ejection fraction (<35%) commonly

applied to ischemic cardiomyopathy is not useful in amyloid cardiomyopathy where decreased ejection fraction is a late finding and indicative of advanced disease and increased mortality due to low output and pump failure. Recent studies have cast increasing doubt on the wisdom of generalizing decreased ejection fraction as a risk stratifier for SCD in patients with heart failure due to other causes, specifically those with non-ischemic cardiomyopathies(23) and heart failure with preserved ejection fraction (24). At this time, patients with amyloid cardiomyopathy are without appropriate risk stratification metrics and are at risk for inadequate treatment and at increased risk for SCD.

The prognostic value of non-sustained VA, another traditional risk factor for SCD in ischemic cardiomyopathy, is also controversial in amyloid cardiomyopathy. Long term outpatient monitoring of both supraventricular and ventricular arrhythmias for prognostic implications in relation to other diagnostic modalities is instrumental in understanding the disease process and providing appropriate therapy.

Currently, the balance of data does not support ICD implantation in amyloid cardiomyopathy (7). However, some studies have demonstrated that ventricular arrhythmias resulting in SCD can be successfully treated with defibrillation, hypothesizing that this treatment may be more successful in earlier stage disease (8,26,27). SCD in late stage disease has been hypothesized to be due to electromechanical dissociation or bradycardia mediated asystole for which an ICD would not be beneficial (25)(8,18). The Mayo clinic staging system based on cardiac biomarkers has been validated and is used to stratify severity of disease (early vs late stage) in TTR-wt cardiomyopathy. The reported 4 year survival estimates of patients with Mayo stage I (TnT <0.05ng/ml and NT BNP <3000 pg/mL), II (either TnT >0.05 ng/ml or NT BNP >3000 pg/mL), and III (TnT >0.05 ng/ml and NT BNP >3000 pg/mL) TTRwt amyloidosis was 57%, 42%, and 18%, respectively (28). Those patients with advanced amyloid cardiomyopathy may have estimated survival less than a year due to heart failure and should be excluded from ICD whereas those with earlier stage may still have added survival benefit. We hypothesize that the occurrence and treatibility of ventricular arrhythmias is dependent on disease progression and may be a phenomena of earlier stage disease. Monitoring at all stages of CA disease to understand arrhythmia risk at each stage is instrumental in understanding the true prevalence and treatment of arrhythmias.

Patients with CA and conduction disease undergo pacemaker implantation for standard guideline criteria. However, bradycardia has been implicated as a mechanism for SCD. Bradycardia leading to asystole has been postulated to be a pre-terminal event reflecting an irreversible sick myocardium (8). A second hypothesis is that the reduced cardiac output associated with bradycardia might be sufficient to induce global ischemic stunning of the heavily infiltrated ventricular myocardium resulting in decompensation and pulseless electrical activity (PEA) arrest(8). In a study of AL amyloidosis patients monitored with ILR, one patient with severe bradycardia who underwent early pacemaker implantation survived. Therefore, it is possible that prophylactic pacemaker implantation into healthier myocardium may prevent SCD due to bradycardia, and treatment with disease modifying therapies can prevent further disease progression. Furthermore, a recent study of prophylactic pacemaker insertion in patients with TTR patients with a genetic variant associated with increased risk of conduction disorders showed a reduction in major cardiac

events over a 45 month follow up (29). The proposed study would permit improved understanding of the initiation of bradycardia, correlating to stage of disease and clinical imaging; helping to further elucidate the pathophysiology of bradycardia and heart block in CA.

#### 1.4.2 Anticipated Risks

Biomonitor 3 is an FDA approved device and will be used in accordance with approved FDA usage. Risks have already been assessed for this device and deemed acceptable for this medical application.

Risks for the BioMonitor 3 are minimal but include risk of bleeding and discomfort on insertion, infection, and malfunction. The BioMonitor 3 demonstrated excellent sensitivity for all types of arrhythmias, combined with a low false detection rate.

List of Anticipated Risks:

- Discomfort at time of insertion
- Infection
- Bleeding

False detection is a minimal risk. The BioMonitor 3 has demonstrated excellent sensitivity for all types of arrhythmias, combined with a low false detection rate.

#### **1.4.3** Potential Benefits

We hypothesize that arrhythmogenesis and SCD risk in this population is influenced by CA stage rather than reduced left ventricular ejection fraction, which is a marker of late disease and increased mortality due to heart failure, bradycardia, or asystole, rather than SCD due to VA. The purpose of this study is to identify TTR-wt cardiac amyloidosis patients at risk for bradycardia or SCD due to VA who may benefit from PPM or ICD, and to determine whether monitoring may be appropriate as standard of care to identify the subgroup of patients who will benefit from PPM or ICD.

## 2 Study Objectives

Listed below are the specific aims/objectives for this study.

**Specific Aim 1**: Burden of conduction system disease and arrhythmias, specifically sinus node dysfunction, high grade heart block, and AF and VA, which will identify those who might benefit from a PPM or ICD

**Specific Aim 2**: Mechanism of SCD (asystole, pulseless electrical activity, or sustained VA) and whether this is different in early vs. late stage amyloidosis.

**Specific Aim 3**: Risk factors for SCA and more specifically whether bradycardia or VA predict SCD, or whether there are imaging or clinical characteristics that predict SCA **Specific Aim 4**: Utility of long term ECG monitoring in TTR-wt cardiomyopathy

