#### 4.5 Description

Biomonitor 3 is a programmable, subcutaneous insertable monitor able to record subcutaneous ECGs (sECGs) and other physiological parameters.

The Biomonitor 3 is designed to automatically record the occurrence of arrhythmias in a patient. Arrhythmia may be classified as atrial fibrillation (AF), bradyarrhythmia, asystole, sudden rate drop, or high ventricular rate. In addition, the Biomonitor 3 can be activated by the patient to record cardiac rhythm during symptomatic episodes.

The Biomonitor 3 system consists of three main components:

 Biomonitor 3 insertable cardiac monitor - The Biomonitor 3 is a small, leadless device that is typically inserted under the skin, in the chest. The device uses two electrodes on the body of the device to continuously monitor the patient's subcutaneous ECG. The device memory can store up to 30 min of subcutaneous ECG (sECG) recordings from automatically detected arrhythmias and up to 30 min of sECG recordings from patient-triggered episodes. When a patient experiences symptoms, the sECG recordings can be manually triggered by placing the Remote Assistant III over the Biomonitor 3. The insertable monitor is provided preloaded in an insertion tool. An incision tool is also provided.

Note - The Biomonitor 3 subcutaneous ECG may differ from a surface ECG due to differences in electrode separation and device placement in the body. Biomonitor 3 detects a subcutaneous ECG from a pair of electrodes. These signals are filtered in two different ways. For detection of QRS complexes, the signals are filtered with a passband of 10-40 Hz in order to suppress T-waves, artifacts, and baseline drift at low frequencies, and myoptentials and EMI at high frequencies. The resulting signal is appropriate for QRS detection as other components of the signal have been suppressed. This signal naturally does not have a typical ECG morphology due to the bandpass. For waveform display (real-time streaming sECG with the physician's programmer and snapshots for review by the physician), a different passband is 0.5 – 40 Hz, which is designed to retain morphological features of a typical ECG while still rejecting large low frequency artifacts and baseline drift.

- 2. BIOTRONIK Renamic / ICS 3000 Programmer The programmer is used to set up the Biomonitor 3 to detect arrhythmias. It also allows you to view, save, or print the stored information.

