#### Home Monitoring for arrythmias

Telemetry tracings from the implantable monitor will be reviewed monthly or whenever an event occurs and/or a patient transmits data due to symptoms via remote assistance.

Default transmission is data sent daily between 1:00AM and 2:00AM regardless of events. If there is a problem with transmission the device will alert the physician within 24 hours and this will help to maintain compliance of transmission.

If no events occur the device will be interrogated prior to explantation at the end of the 6 month monitoring period.

The study investigators will be responsible for telemetry review. The patient's treating cardiologist will be notified of events of clinical significance. Treatment of the arrhythmias will be based on current clinical guideline recommendations for bradycardia and VA. Clinical follow up will occur via standard of care clinical visits.

SCD is defined as sudden and unexpected death within 1 hour of cardiac symptoms in the absence of progressive cardiac deterioration, unexpected death during sleep, or unexpected death within 24 hours after last being seen alive. Study participants who experience SCD while monitored and are successfully resuscitated after life-threatening VA will receive an implantable cardioverter defibrillator based on current clinical guidelines. These and other arrhythmic events recorded by the implantable monitor, or SCD that cannot be successfully resuscitated, will be considered events of interest and NOT adverse events, as these are not a consequence of monitoring via the implantable device.

At the end of the 6 month monitoring period, the device will be explanted. Participants will be offered the choice to retain the device until battery end of life if clinically indicated. However, patients who opt to continue monitoring will be informed that their insurance

company will be billed for clinically indicated monitoring and explantation outside the study time frame.

For any patients who expire during the study monitoring period, the terminal rhythm of participants who die will be reviewed remotely via the Biotronik website irrespective of whether the monitor can be retrieved. Patients will be informed of this possibility during the consent process.

For stage III patients with existing ICD or pacemakers, rhythm monitoring will be obtained from the device over a 6 month timeframe and may be retrospective if applicable.

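### Aim 2 needs deaths sorted into asystole, PEA and sustained VA, but the terminal rhythm on a subcutaneous ECG cannot establish PEA and may not show how the event began

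*Combined protocol and SAP*

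**What the plan says.** - **Section 2, Aim 2** names three mechanisms, "Mechanism of SCD (asystole, pulseless electrical activity, or sustained VA", and asks whether they differ between early and late stage disease.
- **Section 5, Home Monitoring**, gives the step for deaths: "the terminal rhythm of participants who die will be reviewed remotely via the Biotronik website irrespective of whether the monitor can be retrieved". The same section has tracings reviewed monthly, at events, and when a patient transmits for symptoms.
- **Section 4.5** describes the recorder: "The device uses two electrodes on the body of the device to continuously monitor the patient's subcutaneous ECG". It is also "able to record subcutaneous ECGs (sECGs) and other physiological parameters", but none of these parameters is named as a measure of pulse, pressure or perfusion. Its detection classes are: "Arrhythmia may be classified as atrial fibrillation (AF), bradyarrhythmia, asystole, sudden rate drop, or high ventricular rate". Storage is limited: "The device memory can store up to 30 min of subcutaneous ECG (sECG) recordings from automatically detected arrhythmias".
- **Section 5** defines SCD by timing and circumstance. Deaths in sleep and deaths up to a day after the patient was last seen both count. Section 3.2 adds resuscitated arrest to the endpoint.
- **Section 5** also says that rhythm data for stage III patients with an existing ICD or pacemaker come from that device, possibly retrospectively.
- **Section 6.2** includes in the primary hypothesis that SCD is due to asystole rather than ICD-treatable VA.

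Neither section 5 nor section 6 gives a rule for assigning mechanism, a rule for labelling PEA, or an undetermined class.

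**The concern.** PEA is organised electrical activity without a pulse. An ECG shows the electrical half of that definition and not the other half, so one of Aim 2's three categories has no described measurement.

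The terminal rhythm also answers a different question from mechanism. Aim 2 and the rationale in section 1.4.1 are about how the death came about. The last rhythm shows how it ended.

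What is at stake is the mechanism split by stage. Section 6.1 presents the pilot as the basis for larger trials. If the labels are unreliable, or unreliable to different degrees in the two stage groups, the split could mislead the design of those trials.

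**Working it through.** The plan gives no figure to reproduce on this point. The check sets what each label needs against what is collected, then looks at direction and scale.

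**1. Label against source**

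| Aim 2 category | What the label needs | What the plan describes |
|---|---|---|
| Asystole | ECG | A device class, visible on the tracing |
| Sustained VA | ECG covering the onset | No class of that name; high-ventricular-rate episodes are stored and investigators read tracings, but the last rhythm may come later |
| PEA | ECG plus evidence of no pulse | ECG only; no device class and no pulse signal described |

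For unwitnessed deaths, which the SCD definition includes, a pulse check at onset is unlikely to exist.

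**2. Initiating against terminal rhythm.** Section 1.4.1 offers two hypotheses. In one, "Bradycardia leading to asystole has been postulated to be a pre-terminal event reflecting an irreversible sick myocardium". In the other, bradycardia lowers output, stuns the ventricle and ends in PEA arrest. Both start with bradycardia and then diverge. The final rhythm alone therefore does not identify the start, and a VA that degenerates before the last strip would not be seen there either.

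**3. Direction of the error (illustration; all inputs assumed).** Let a and p be the true asystole and PEA shares, m the share of PEA deaths labelled asystole, and c the share of deaths read from a pacing device that hides asystole completely. Then

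recorded asystole share = (1 − c) × (a + m × p).

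With a = p = VA share = 1/3:
- c = 0, m = 0: 1/3 = 33%, the true value
- c = 0, m = 0.5: 1/3 + 1/6 = 50%
- c = 0, m = 1: 1/3 + 1/3 = 67%
- c = 0.5, m = 0.5: 0.5 × 0.50 = 25%
- c = 0.5, m = 1: 0.5 × 0.67 = 33%

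The recorded share can be above, equal to or below the truth. The documents give neither m nor c, so they do not fix the sign. If c is larger in stage III, the error differs between the groups that Aim 2 compares.

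**4. Scale (context only).** Inputs are four-year survival of 57%, 42% and 18% for stages I, II and III (section 1.4.1) and 25 patients per group (section 4). Six months is 1/8 of four years, so with a constant hazard the six-month risk is 1 − S^(1/8):
- Stage I: 1 − 0.57^(1/8) = 6.8%
- Stage II: 1 − 0.42^(1/8) = 10.3%
- Stage III: 1 − 0.18^(1/8) = 19.3%

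Expected deaths are 25 × 6.8% = 1.7 (early group all stage I) to 25 × 10.3% = 2.6 (all stage II), plus 25 × 19.3% = 4.8 in stage III. The total is 6.5 to 7.4. If 25% to 75% are sudden (assumed), that is 6.5 × 0.25 = 1.6 to 7.4 × 0.75 = 5.5 SCDs.

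**The case against.** The strongest reply is that no text makes the last rhythm decide the label. Section 5 says only that it will be reviewed, and event tracings are reviewed too. High ventricular rate is an automatic detection class, so a death starting as VA may leave a stored episode. Investigators, not the device classes, would make the call. Hospital records are source documents (section 8.2), and resuscitated arrests may come with pulse data. This stands, and it limits the point to what is described: no procedure links these sources to a mechanism label.

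Three stronger readings are tempting, and the documents do not support them.

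- **A reader might infer that the method over-assigns asystole and so favours the hypothesis in section 6.2.** PEA could instead be logged as bradyarrhythmia or sudden rate drop, or trigger no strip, and pacing could hide asystole. The asystole clause of the hypothesis is grammatically incomplete, and its next sentence allows VA leading to SCD earlier in disease. The test named there compares arrhythmia burden, not mechanism of death.
- **A reader might infer that ICD-treatable and untreatable deaths cannot be told apart.** Section 1.4.1 puts electromechanical dissociation and bradycardia-mediated asystole on the same side, as deaths an ICD would not help. Confusing PEA with asystole does not cross that line. Only VA read as asystole would, and nothing shows that this will happen.
- **A reader might take the effect of one wrong label as the size of the bias.** One label is 1/5.5 = 18% to 1/1.6 = 61% of the split, but that is simply one over a small assumed count and holds under any classification method.

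**Conclusion.** The point holds as a measurement gap. Aim 2 requires a PEA category that the described source cannot establish by itself, and a mechanism that the terminal rhythm may not show. Misclassification is likely. Its size and direction are unknown, and it may differ by stage because of the device-read stage III patients.

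The count of 6.5 to 7.4 deaths assumes a constant hazard, the protocol's historical survival, and prospective follow-up of all 50 patients. Newer therapy would lower it, and so would retrospective windows, since a patient enrolled afterwards was alive throughout. The sudden fraction is an assumption. These numbers show why each label matters in a small pilot. They do not show that any label is wrong.

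The change should be made, because a better method is available from material the study already collects.

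**What to change.** In section 5 and Aim 2, for every death and every resuscitated arrest:

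1. Record the **initiating rhythm** from stored episodes within a look-back window fixed in advance: sustained VA, bradycardia or heart block, primary asystole, no initiating arrhythmia, or onset not recorded. The window is needed because AF and bradycardia are expected background findings. The last class is needed because storage is limited and transmission can fail (section 4.7).
2. Record the **terminal rhythm** as a separate variable.
3. Assign **PEA** only when an organised rhythm coincides with pulselessness documented in existing clinical or resuscitation records. Otherwise use *organised rhythm, pulse unknown* or *indeterminate*.
4. Report the **data source** with each label, Biomonitor 3 or existing pacemaker/ICD, so that differences by stage can be read against it.

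The cost is protocol wording, a few CRF fields and some record review. No patient procedure is added. A number of deaths will be left indeterminate, particularly unwitnessed ones, and the mechanism table will be thinner for it.
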